- To determine the variability of glucose excursion, level and peak and the recovery time in the three-hour postprandial period.
- To describe comparisons between all the above measurements and the variables of sex, age, disease duration, BMI, HbA1c, insulin dose/sensitivity and insulin regimen.
- To describe comparisons between all the above measurements and the glycaemic load and composition of the test and control meals.

Study design

This is a quantitative study. Dexcom CGM data will be collected for the period of recording. Participants will be asked to test three breakfast meals on two occasions and submit a postprandial questionnaire after each test meal to confirm it has been tested. The postprandial period will be three hours following the end of the breakfast test meal. The test meal recipes

will be provided by the chief investigator. The dietary composition of the meals has been analysed using the Nutritics dietary analysis programme (Nutritics, 2022). The glycaemic index and load of the meals is estimated from the Nutritics programme which uses available data from the international tables of glycaemic index and glycaemic loads (Atkinson *et al.* 2008; 2021). Most foods were based on average composition across different brands. For the added fibre bread used in test meal 3, an average of three known brands was used calculated by the chief investigator. The meals will be taken in the home environment with the food provided by the families. The participants will be asked to take the test meal on a day when their CGM reading is between 4-10mmol/l and when there has been no nocturnal hypoglycaemia on the night before the planned test. The participants will act as their own control. They will be asked to complete a postprandial questionnaire for control meals as well. The control meals will be their usual breakfast of choice. The study duration, commencing with the recruitment of the first participant and ending when data has been fully described, is anticipated to be two years.

Participants

Eligibility criteria

- Children and young people aged between 5-17 years
- Diagnosis of type 1 diabetes for a minimum of one year
- On multiple daily injections (MDI) together with carbohydrate counting or Continuous Subcutaneous Insulin Infusion (CSII) using either open or closed loop systems.
- Use Dexcom continuous glucose monitoring (CGM) on a regular basis
- Have a Dexcom Clarity account and use the Clarity App

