The test meals are based on foods children and young people enjoy eating. There are three meals. Test meal one includes a high glycaemic index cereal meal with milk and has a high glycaemic load (> 20), test meal two is the same cereal meal with a high glycaemic load (>20) with addition of 10g protein and test meal three has a medium glycaemic load (10-20). For test meals one and two there are three portion size options to meet age appropriate requirements and appetites. The participants will be able to choose from two different cereals for test meal 1 and a choice of protein sources for test meal 2. They will be asked to keep to the same choice of cereal and protein source for the repeat meal. They will be asked to consume at least 75% of the meal to ensure the threshold of the glycaemic load is met. The

instructions and details of the test meals are presented in Appendix 11. The control meals will be the participant's usual breakfast of choice.

Participants will be asked to follow their usual insulin regimen as advised by their diabetes team i.e. their usual insulin dose and dose timing. For both test and control meals participants will be asked to avoid any further food intake during three-hour postprandial period other than carbohydrate adjustments required to treat any hypoglycaemia. Participants will also be asked to avoid drinks except water or carbohydrate free juices. They will also be asked to avoid physical activity of more than 30 minutes in duration. To minimise disruption to their normal daily activities, they will be advised to test the meal on a day when there is no planned physical activity i.e. a school day with no morning physical education. The CGM data will be collected throughout this time as discussed above.

Postprandial Questionnaire

The participants will be asked to complete a postprandial questionnaire using 'online survey'. This includes questions about the meal and the three-hour postprandial period. The questionnaire is presented in Appendix 10. They will be asked to wait a minimum of three hours before answering and submitting the questionnaire. They will be encouraged to complete it on the same day as the test or control meal.

Outcome measures

Primary and secondary outcome measures will be based on international guidelines and consensus DiMeglio *et al.* 2018; Battelino *et al.* 2019) of the metrics and target glucose levels to be used in CGM analysis in clinical practice. These are agreed to be:

Metrics:

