It is anticipated that new data, arising from the study, and the associated intellectual property will be owned jointly by the University of Stirling and NHS Highland with a sharing agreement.

Destruction of data

The Dexcom Clarity clinic only stores CGM data for three months. Once these data have been collected for the period of the study, the Dexcom research clinic will be closed. Any transferred data will be stored on the NHS Highland secure remote server for 10 years before being deleted. Personal data (emails addresses, artificial identifiers, dates of birth will be deleted 6-12 months after the study ends).

Definition of end of study

The study will end when all the participants have completed the test and control meals and submitted their questionnaire responses and their CGM data for the period of the meals has been exported and they have been removed from the Clarity clinic.

Expected outcomes

The aim of this study is to describe the distribution and dispersion of glucose variability and postprandial hyperglycaemia after test meals at breakfast and establish comparisons of these between variables obtained from baseline information and nutrient analysis. It is hoped this

will provide evidence of the impact of high and medium glycaemic load breakfast meals have on glycaemic response in children and young people who have T1D. It is also hoped the study will provide evidence of the impact additional protein has on glycaemic response when taken as part of a mixed high glycaemic load meal.

This will increase the knowledge of diabetes educators, patients and families and ensure diabetes education includes evidence-based information on how to minimise postprandial hyperglycaemia at breakfast time.

Dissemination of results

It is anticipated that one paper will be submitted for publication. The proposed journals for publication include:

- *Pediatric Diabetes*
- *Diabetic Medicine*
- *Diabetologia*
- *Diabetes Technology & Therapeutics*
- *Acta Diabetologica*.

Ethical considerations

This study has been reviewed and provided a favorable opinion by... *to be added when obtained*

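### The main text sets no minimum intake for the added protein that alone separates test meal 2 from test meal 1

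*Combined protocol and SAP*

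**What the plan says.** The Test and control meals section builds the second test meal from the first: "test meal two is the same cereal meal with a high glycaemic load (>20) with addition of 10g protein". Participants pick the size and the protein food: "For test meals one and two there are three portion size options to meet age appropriate requirements and appetites", and there is "a choice of protein sources for test meal 2". The intake rule follows: "They will be asked to consume at least 75% of the meal to ensure the threshold of the glycaemic load is met". It is a request about the meal as a whole, and the only reason given for it is glycaemic load.

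Under Study design, "The meals will be taken in the home environment with the food provided by the families", and participants are to "submit a postprandial questionnaire after each test meal to confirm it has been tested". Of the questionnaire itself, the Postprandial Questionnaire section says "This includes questions about the meal and the three-hour postprandial period". Its items are in Appendix 10 and the meal instructions are in Appendix 11. Neither appendix is in the text available for review.

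The Data analysis section does not say how an occasion with partial intake is handled. Expected outcomes names protein as a question of interest: "It is also hoped the study will provide evidence of the impact additional protein has on glycaemic response".

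**The concern.** The rule protects the feature that meals 1 and 2 share (a high glycaemic load) and leaves unprotected the feature that distinguishes them (the protein). A participant who eats the cereal and leaves some or all of the protein can still have done what was asked. On that occasion meal 2 moves towards meal 1, and it becomes meal 1 if no protein is eaten.

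The meal 2 versus meal 1 contrast is the only one in the design that isolates added protein. If such occasions occur and intake is not recorded by component, a small or null result could mean either that 10 g of protein does little or that the protein was not fully eaten. The data could not tell these apart. The background section says there appears to be no evidence on protein as prevention at breakfast, so a diluted null could carry weight.

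**Working it through.** **Inputs from the document.** Intake rule 75% of the meal; added protein 10 g (both Test and control meals). Effect size 0.15, four measurements, correlation 0.5, alpha 0.05, power 0.80, N = 64 (all Sample size). The document gives no meal weights, protein-item weights or rates of partial intake. Values for these below are assumptions.

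**1. The plan's own figure.** For a within-factor repeated-measures ANOVA, the noncentrality is λ = f²·N·m/(1 − ρ) = 0.0225 × N × 4/0.5 = 0.18N. The smallest N with 80% power is 62 (λ = 11.16), or 64 as a multiple of four groups; power at 64 is 0.81. The figure of 64 reproduces. It is sized for the overall four-meal test, not for meal 2 versus meal 1, and serves below only as a number of pairs.

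**2. Least protein that still meets the rule.** Let s be the protein item's share of the meal, with the item served separately. The rule lets 25% of the meal be left. If everything left is the protein item, protein eaten = 10 × max(0, 1 − 0.25/s) g.

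| Share s | Least protein eaten (g) |
|---|---|
| 25% or less | 0 |
| 30% | 1.7 |
| 35% | 2.9 |
| 40% | 3.8 |
| 50% | 5.0 |
| 60% | 5.8 |

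If the rule is judged by its stated purpose, glycaemic load, a protein source with little or no carbohydrate adds almost nothing. The rule is then met with 0 g at any share.

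**3. Is a share of 25% or less plausible?** By weight, with M the cereal plus milk and P the protein item, P ≤ 0.25(M + P) gives P ≤ M/3. With M assumed at 155 to 250 g, the limit is 155/3 = 52 g to 250/3 = 83 g. The weight of food that supplies 10 g protein is 10/0.25 = 40 g, 10/0.20 = 50 g, 10/0.125 = 80 g or 10/0.10 = 100 g for assumed protein contents of 25%, 20%, 12.5% and 10%.

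- 40 g and 50 g items can be left entirely across the whole range.
- An 80 g item can be left entirely only if M is at least 240 g.
- A 100 g item would need M of at least 300 g, which is outside the range.
- The largest share in the range is 100/(155 + 100) = 39%, where the least protein eaten is 10 × (1 − 0.25/0.392) = 3.6 g.

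Leaving all of the protein is therefore possible for compact sources but not for all. Leaving more than half is possible in every case assumed here.

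**4. Effect on the contrast.** If a fraction q of meal 2 occasions contain no protein, unrelated to glucose response, the expected contrast is (1 − q) times the true one. For illustration, take 64 pairs and a standardised paired difference of 0.356, chosen to give 80% power at full intake (noncentral t, two-sided 0.05).

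| q | Effect remaining | Power at 64 pairs | Pairs for 80% power |
|---|---|---|---|
| 0 | 100% | 80% | 64 |
| 10% | 90% | 71% | 79 |
| 20% | 80% | 61% | 99 |
| 30% | 70% | 50% | 129 |

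**5. Is there a later safeguard?** In the main text, submitting the questionnaire confirms that a meal was tested, and the analysis section has no step that flags, excludes or adjusts for partial intake.

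**The case against.** The strongest reply is that the detail may sit elsewhere. The main text sends the reader to Appendix 11 for meal instructions and Appendix 10 for the questionnaire, and a component-level instruction or a question on leftovers would naturally be there. This stands. A reader might infer that the study has no other intake rule at all, but the documents support only the statement that the main text gives no other.

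Second, nothing says that the protein is served apart from the cereal. If it is mixed in, eating 75% of the meal delivers about 0.75 × 10 = 7.5 g and the gap largely closes. This also stands, so the point is conditional on a separate item.

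Third, a reader might infer that the protein is the part most likely to be left, so that meal 2 in practice turns into meal 1. The documents do not support this. Participants choose the protein source and the portion size, the meals are built on foods that children like, and people with an intolerance to the meals or difficulties with food are excluded. Against that, the section on recruitment and consent accepts that a disliked meal need not be eaten, so incomplete intake is foreseeable. Its frequency and pattern are unknown.

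Fourth, the 75% is a request, and no passage makes it a condition for entering the analysis. It would be wrong to say that an inclusion rule admits protein-free occasions. With no rule, nothing shown removes or identifies them.

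Finally, the study's stated aim is descriptive, and comparing meals as offered is a legitimate question for dietary advice. This limits the severity. It does not remove the need to know how much protein was eaten when a result is attributed to protein.

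**Conclusion.** The concern holds in a limited form. In the main text, the one stated intake rule guards glycaemic load and sets no minimum for the 10 g of protein that defines test meal 2. With a separately served item, the rule can be met with 0 g eaten at a share of 25% or less, and with 5 g or less at a share of up to 50%. Any such occasions would bias the meal 2 versus meal 1 contrast towards no difference.

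The size of that bias cannot be estimated from the documents. The 10% to 30% figures show how dilution works and are not a forecast. They assume all-or-nothing omission unrelated to glucose response. Nor do the documents support a conclusion that a null protein result would be an artefact. What they support is that such a result could not be interpreted with confidence unless intake is captured by component. The change should be made before test meals begin, because component intake may not be recoverable later.

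**What to change.** In the Test and control meals section, and in Appendices 10 and 11 if not already there:

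- For test meal 2, ask for at least 75% of the cereal and at least 75% of the protein source (0.75 × 10 = 7.5 g protein).
- Have the questionnaire record the proportion eaten of each separately.

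In the Data analysis section:

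- Keep all occasions in the main analysis, and report protein eaten in grams by occasion.
- Add one prespecified supplementary meal 2 versus meal 1 contrast limited to occasions meeting both minima. Label it exploratory, because it selects on intake after randomisation.

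The cost is a reworded instruction, one extra questionnaire item and one supplementary analysis. A few more occasions will be classed as not meeting the rule, and the supplementary contrast may carry selection bias. The main estimate will still contain whatever dilution remains; the change makes that dilution less likely and measurable. If the appendices already cover intake by component, only the main text and the analysis section need aligning.

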- Mean glucose
- Glucose variability (GV) % coefficient of variation (COV) target $\leq 36\%$
- Time in range (TIR) % and time spent between 3.9-10mmol/l
- Time above target (TAR) % and time spent $>10.1\text{-}<13.9\text{mmol/l}$ and $>13.9\text{mmol/l}$
- Time below range (TBR) % and time spent 3.0-3.8mmol/l and $<3\text{mmol/l}$

Target glucose levels:

- TIR - % of readings $>70\%$ or 16hr 48min
- TAR - % of readings $<25\%$ or $<6\text{hr}$ high and $<5\%$ 1hr 12min very high
- TBR- % of readings $<4\%$ or $<1\text{hr}$ low and $<1\%$ or $<15\text{min}$ very low

Primary outcome measure:

- Mean glucose (mmol/l) in the three-hour postprandial breakfast period calculated from the CGM measurements at 5 minutes intervals.

Secondary outcome measures – post prandial period:

- Number and percentage who had pre-prandial glucose in target, mean peak glucose level (mmol/l), mean time to peak (mins), mean time to recover (to pre-prandial levels) (mins) in the three-hour postprandial breakfast period
- TIR, TBR and TAR (% and time) in the three-hour postprandial breakfast period
- Comparisons of the above measurements between cohorts and breakfast test meal compositions.

Data analysis

This will be a mix of univariate, bivariate and multivariate analysis as this is best suited to describing, summarising and visualising these data. Outputs will include the distribution of glucose levels post-breakfast to determine the spread and dispersion of the data.

Safety considerations

Recruitment/consent

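### The glucose bands are not exhaustive: readings of 10.1 and 13.9 mmol/l fall in no band, so time above range is slightly understated

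*Combined protocol and SAP*

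**What the plan says.** All the definitions are in the Outcome measures section of the combined protocol and SAP.

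- **In range (Metrics):** "Time in range (TIR) % and time spent between 3.9-10mmol/l".
- **Above range (Metrics):** "Time above target (TAR) % and time spent" in two bands, >10.1 to <13.9 mmol/l and >13.9 mmol/l. Every inequality is strict.
- **Below range (Metrics):** 3.0 to 3.8 mmol/l, and <3 mmol/l.
- **Target glucose levels:** each target is a percentage of readings with a clock-time equivalent: >70% (16 h 48 min) in range; <25% (6 h) and <5% (1 h 12 min) above; <4% (1 h) and <1% (15 min) below.
- **Secondary outcomes:** "TIR, TBR and TAR (% and time) in the three-hour postprandial breakfast period", with comparisons between cohorts and between meal compositions.

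The primary outcome is mean glucose over the same three hours, from readings every 5 minutes. The Data analysis section gives no rule for a reading that fits no band.

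**The concern.** Time below, in and above range should split each window completely, so that every reading counts once and the shares total 100%. On the low side the cut-points abut at 0.1 mmol/l steps (<3, 3.0 to 3.8, 3.9 upward). On the high side they do not. The range ends at 10, the next band starts strictly above 10.1, and neither upper band includes 13.9.

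Both lost values lie above 10 mmol/l, so literal use of the rule can only understate time above range. Postprandial hyperglycaemia is what the study aims to describe, and time above range is compared between meals. If the rule is left as it stands, the analyst has to choose how to repair it, and different unrecorded repairs give slightly different results.

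**Working it through.** **Inputs.** Band limits, targets, the three-hour window and the 5-minute interval come from Outcome measures. The 0.1 mmol/l resolution is an assumption, taken from how the plan writes its cut-points. The glucose distribution is also an assumption, because the plan gives no mean or SD.

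**1. The plan's clock-time figures.** Percentage × 24 h:

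| Target | × 24 h | Plan states | × 180 min |
|---|---|---|---|
| 70% | 16 h 48 min | 16 h 48 min | 126 min |
| 25% | 6 h | 6 h | 45 min |
| 5% | 1 h 12 min | 1 h 12 min | 9 min |
| 4% | 57.6 min | 1 h | 7.2 min |
| 1% | 14.4 min | 15 min | 1.8 min |

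The stated figures are correct 24-hour equivalents, the last two rounded up. The final column is for orientation only.

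**2. Coverage of the bands.** Each value from 2.0 to 29.9 mmol/l, in steps of 0.1, was tested against the five bands as written. Exactly two values, 10.1 and 13.9, fall in none. No value falls in two.

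**3. Effect on one window.** 180 / 5 = 36 readings. Each unclassified reading removes 1/36 = 2.8 percentage points from that window's total.

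**4. Expected loss.** Assume one-decimal readings from a normal distribution with mean 9, 10 or 11 and SD 2.5, 3 or 3.5 mmol/l. The share in no band is P(10.05 to 10.15) + P(13.85 to 13.95).

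- Smallest (mean 9, SD 3.5): 1.09% + 0.43% = 1.51% after rounding, or 180 × 0.0151 = 2.7 min.
- Largest (mean 11, SD 2.5): 1.50% + 0.81% = 2.31%, or 180 × 0.0231 = 4.2 min.
- As a share of all time above range, dividing by P(>10.05): 1.91 / 60.7 = 3.1% (mean 11, SD 3.5) to 1.68 / 33.7 = 5.0% (mean 9, SD 2.5).
- With one pooled upper band, only 10.1 is lost: 1.1% (mean 9, SD 3.5) to 1.6% (mean 10, SD 2.5).

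**5. Effect on a contrast, same model, SD 3.** Moving the mean from 9 to 11 raises the share above range from 1 − Φ((10.05 − 9)/3) = 36.3% to 1 − Φ((10.05 − 11)/3) = 62.4%, a difference of 26.1 points. The loss rises from 1.6% to 2.1%, so the contrast shrinks by about 0.5 points.

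**6. Finer resolution.** If readings carry more decimals, values between 10 and 10.1 and between 3.8 and 3.9 are also unclassified. The upper gap is again 0.1 mmol/l wide, so the loss there is of similar size.

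**The case against.** The best defence is that this is a wording slip of little consequence. The expected loss is less than one 5-minute reading per window. The listed outcome is time above range as such, so 13.9 would naturally be counted and only 10.1 is in doubt. The same rule applies to every meal, so most of the loss cancels in comparisons, as step 5 shows. The mean and SD are not protocol figures. All of this stands and limits the size of the point. It does not make the bands exhaustive, and the plan offers no rule that does.

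A second fair objection is that the precision of the exported readings is not stated in the text. The section on Dexcom CGM data refers to an example in Appendix 12, which is not among the documents at hand. This affects the remedy: changing the band to 10.1 to 13.9 inclusive closes the gap only for one-decimal data.

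A reader might also infer that the plan judges three-hour results against 24-hour limits, since 16 h 48 min can never be reached in 180 minutes and <6 h is always met. The documents do not support that. The targets are introduced as guideline figures for clinical practice, and no listed outcome is attainment of a clock-time target. The percentages beside them carry over to three hours, and the three-hour results are already specified as percentage and time. The first objective also covers diurnal and nocturnal variability, so longer-period targets are not out of place in the list.

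**Conclusion.** The point holds for the bands. As written they leave 10.1 and 13.9 mmol/l unclassified at one-decimal resolution, and more values if the data are finer. Time above range is understated, and the total falls below 100% only in windows that contain such a reading. Under the assumed normal distributions the loss is about 1.5 to 2.3% of readings, or about 1.1 to 1.6% if time above range is pooled. The effect is confined to secondary outcomes, is small in between-meal contrasts under that model, and does not touch the primary outcome.

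It would go too far to say that hyperglycaemia is materially under-reported, or that the metrics fail to scale to three hours. Percentages and minutes can both be computed in the window. Only the clock-time targets belong to 24 hours, and that is a matter of labelling. This is a minor error in a stated rule, worth correcting before analysis.

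**What to change.** In the Metrics list, define the analysis bands contiguously: <3.0; 3.0 to <3.9; 3.9 to 10.0 inclusive; >10.0 to 13.9 inclusive; >13.9 mmol/l. This keeps the in-range limits and the highest band as the plan has them, and it works at any decimal resolution. Add a programmed check that time below, in and above range totals 100% of the available readings in every three-hour window.

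As a labelling remark, mark the five clock-time targets as 24-hour figures that are not limits for the 180-minute window.

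The cost is one or two lines of wording and one check in the analysis code. No new data are needed, and neither participant management nor the primary outcome changes.
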